APPENDIX A PERFORMANCE STATUS CRITERIA

ECOG Performance Status Scale		Karnofsky Performance Scale	
Grade	Descriptions	Percent	Description
0	Normal activity. Fully active, able to carry on all pre-disease performance without restriction.	100	Normal, no complaints, no evidence of disease.
		90	Able to carry on normal activity; minor signs or symptoms of disease.
1	Symptoms, but ambulatory. Restricted in physically strenuous activity, but ambulatory and able to carry out work of a light or sedentary nature (e.g., light housework, office work).	80	Normal activity with effort; some signs or symptoms of disease.
		70	Cares for self, unable to carry on normal activity or to do active work.
2	In bed <50% of the time. Ambulatory and capable of all self-care, but unable to carry out any work activities. Up and about more than 50% of waking hours.	60	Requires occasional assistance, but is able to care for most of his/her needs.
		50	Requires considerable assistance and frequent medical care.
3	In bed >50% of the time. Capable of only limited self-care, confined to bed or chair more than 50% of waking hours.	40	Disabled, requires special care and assistance.
		30	Severely disabled, hospitalization indicated. Death not imminent.
4	100% bedridden. Completely disabled. Cannot carry on any self-care. Totally confined to bed or chair.	20	Very sick, hospitalization indicated. Death not imminent.
		10	Moribund, fatal processes progressing rapidly.
5	Dead.	0	Dead.

STUDY DRUG INFORMATION WALLET CARD

You are enrolled on a clinical trial using the experimental study drugs atezolizumab and cobimetinib. This clinical trial is sponsored by the NCI. Cobimetinib may interact with drugs that are processed by your liver. Because of this, it is very important to:

- Tell your doctors if you stop taking any medicines or if you start taking any new medicines.
- Tell all of your health care providers (doctors, physician assistants, nurse practitioners, or pharmacists) that you are taking part in a clinical trial.
- Check with your doctor or pharmacist whenever you need to use an over-the-counter medicine or herbal supplement.

Cobimetinib interacts with a specific liver enzyme called CYP3A4 and must be used very carefully with other medicines that interact with this enzyme.

- Before you enroll onto the clinical trial, your study doctor will work with your regular health care providers to review any medicines and herbal supplements that are considered strong inducers/inhibitors or substrates of CYP3A4.
- Before prescribing new medicines, your regular health care providers should go to a frequently-updated medical reference for a list of drugs to avoid, or contact your study doctor.
- Your study doctor's name is _____
and can be contacted at _____.

APPENDIX C STUDY CHECKLIST FOR CTEP-SUPPORTED EARLY PHASE TRIALS WITH BIOMARKER ASSAYS AND BIOASSAY TEMPLATES

1. Name of marker:

CD8

2. For an integral or integrated assay, indicate the role(s) of the biomarker assay in the trial:

This is an INTEGRATED assay aimed at evaluate the effect of MEK inhibition on CD8+ T cell infiltration in patients with cholangiocarcinoma. Across many tumor types the extent of CD8+ T cell infiltration may predict clinical benefit from treatment with PD-1/PD-L1 blockade (Taube et al. 2014). Increasing CD8+ T cell infiltration is therefore one potential strategy for increasing response rates to anti-PD-1 therapies. In preclinical studies, work from the Mellman group (Ebert et al. 2016) demonstrated that MEK inhibition can reverse T cell signal-driven apoptotic “exhaustive” T cell death within a tumor by blocking the upregulation of certain pro-apoptotic factors resulting in the accumulation of CD8+ T cells within tumors. We postulate that MEK inhibition may represent a novel approach to re-program the tumor microenvironment in a manner that favors responsiveness to PD-L1 blockade.

5. Provide data on the clinical utility of the integral/integrated assay as it will be used in the trial:

Preclinical data demonstrate the potential for synergy between MEK inhibitors and PD-1 checkpoint inhibitors. Several studies have demonstrated that MEK inhibitors upregulate HLA and downregulate certain immunosuppressive mechanisms within the tumor (Kakavand et al. 2015; Liu et al. 2015; Reddy et al. 2016). Additionally, Mellman et al. recently demonstrated that MEK inhibition may also directly potentiate T-cell based anti-tumor immunity. In an animal model, this group showed that MEK inhibition can reverse T cell signal-driven apoptotic “exhaustive” T cell death within a tumor by blocking the upregulation of certain pro-apoptotic factors; this results in the accumulation of CD8+ T cells within tumors. In the aggregate these data provide mechanistic rationale for combination treatment with a MEK inhibitor and an immunomodulator targeting PD-1. These data support the use of CD8+ T cell infiltration as a biomarker that may be relevant to this treatment combination.

Based on previous clinical experience, we anticipate that paired biopsy samples will be successfully obtained in at least 50% of participants. We anticipate obtaining approximately 20 subjects in each treatment arm with paired samples available for analysis, offering 80% power for detecting an increase in CD8+ density equal to 0.8s.d., using a one-sided t-test with alpha=0.05, and more than 90% power for detecting an effect size of 1.0s.d. The change in CD8 density will be captured and reported as a continuous variable, rather than a categorical variable.

As the described biomarker results are experimental in this context and are not currently applicable to the care of the patient, they will not be made available to the treating physicians or patients.

NCI Protocol #: 10139

Protocol Version Date: October 10, 2022

The IHC bioassay template is attached to this protocol.

APPENDIX D IMMUNE-RELATED RESPONSE CRITERIA

Introduction

Increasing clinical experience indicates that traditional response criteria (e.g., Response Evaluation Criteria in Solid Tumors, Version 1.1 [RECIST v1.1] and World Health Organization [WHO]) may not be sufficient to fully characterize activity in the new era of target therapies and/or biologics. In studies with cytokines, cancer vaccines, and monoclonal antibodies, complete response, partial response, or stable disease has been shown to occur after an increase in tumor burden as characterized by progressive disease by traditional response criteria. Therefore, conventional response criteria may not adequately assess the activity of immunotherapeutic agents because progressive disease (by initial radiographic evaluation) does not necessarily reflect therapeutic failure. Long-term effect on the target disease must also be captured. The immune-related response criteria (irRC) are criteria that attempt to do that by enhancing characterization of new response patterns that have been observed with immunotherapeutic agents (*i.e.*, ipilimumab) (Wolchok *et al.*, 2009). (Note: The irRC only index and measurable new lesions are taken into account.)

Glossary

Term	Definition
SPD	sum of the products of the two largest perpendicular diameters
Tumor burden	SPD _{index lesions} + SPD _{new, measurable lesions}
Nadir	minimally recorded tumor burden
irCR	immune-related complete response
irPD	immune-related progressive disease
irPR	immune-related partial response
irSD	immune-related stable disease
irBOR	immune-related best overall response

Baseline Assessment Using irRC

Step 1. Identify the index lesions (five lesions per organ, up to ten visceral lesions and five cutaneous lesions).

Step 2. Calculate the SPD of all of these index lesions:

$$\text{SPD} = \sum_i (\text{Largest diameter of lesion } i) \times (\text{Second largest diameter of lesion } i)$$

Post-Baseline Assessments Using irRC

Step 1. Calculate the SPD of the index lesions.

Step 2. Identify new, measurable lesions ($\geq 5 \times 5$ mm; up to five new lesions per organ: five new cutaneous lesions and ten visceral lesions).

Step 3. Calculate the SPD of the new, measurable lesions.

Step 4. Calculate the tumor burden:

Tumor burden = $SPD_{\text{index lesions}} + SPD_{\text{new, measurable lesions}}$

Step 5. Calculate the change in tumor burden relative to baseline and the change in tumor burden relative to nadir.

Step 6. Derive the overall response using the table below.

Overall Response	Criterion
irCR	Complete disappearance of all lesions (whether measurable or not, and no new lesions) confirmed by a repeat, consecutive assessment ≥ 4 weeks from the date first documented
irPR	Decrease in tumor burden $\geq 50\%$ relative to baseline confirmed by a consecutive assessment ≥ 4 weeks from the date first documented
irSD	Criteria for irCR, irPR, and irPD are not met; does not require confirmation
irPD	Increase in tumor burden $\geq 25\%$ relative to nadir confirmed by a consecutive assessment ≥ 4 weeks from the date first documented

irCR = immune-related complete response; irPD = immune-related progressive disease;

irPR = immune-related partial response; irSD = immune-related stable disease.

Determination of irBOR

Once a patient has completed all tumor assessments, his/her irBOR may be determined:

Condition	irBOR
At least one irCR	irCR
At least one irPR and no irCR	irPR
At least one irSD and no irCR and no irPR	irSD
At least one irPD and no irCR, no irPR, and no irSD	irPD

irBOR = immune-related best overall response; irCR = immune-related complete response;

irPD = immune-related progressive disease; irPR = immune-related partial response;

irSD = immune-related stable disease.

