5.3 Duration of Therapy

In the absence of treatment delays due to adverse event(s), treatment may continue until one of the following criteria applies:

- Disease progression not meeting criteria dosing of study treatment beyond disease progression (see 5.3.1).
- Intercurrent illness that prevents further administration of treatment,
- Unacceptable adverse event(s), as defined in section 6.1.1, or at the discretion of the treating physician,
- Patient decides to withdraw from the study, or
- General or specific changes in the patient's condition render the patient unacceptable for further treatment in the judgment of the investigator.

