5.3.1 Dosing of Study Treatment Beyond Disease Progression

Study treatment beyond disease progression on an imaging scan is allowed for patients on both treatment arms. However, participants who meet criteria for continued treatment must discontinue treatment upon documentation of disease progression on the second scan (relative to the scan that initially showed progression). Patients must also meet all of the following criteria to receive study treatment beyond disease progression:

- Evidence of clinical benefit as assessed by the investigator.
- Absence of symptoms and signs indicating unequivocal progression of disease.
- Absence of tumor progression at critical anatomical sites (e.g., leptomeningeal disease) that are life threatening and cannot be managed by protocol-allowed medical interventions.

- No evidence of clinical deterioration and no evidence of progressive disease at critical anatomical sites (e.g., cord compression) requiring urgent alternative medical intervention.
- Patients treated beyond progression should receive their next follow-up scan 6-8 weeks following the initial assessment of radiological progression.

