J: Baseline scans must be done < 4 weeks prior to randomization. Tumor measurement will be performed with contrast CT chest/abdomen/pelvis. Non-contrast CT chest/abdomen/pelvis or CT Chest and MRI Abdomen/pelvis will be performed in subjects with contraindications or intolerance to contrast dye. Imaging will be repeated every 8 weeks (+/- 4 days), irrespective of dosing schedule or treatment delays. For patients continuing treatment past progression, the subsequent scan should be performed 6-8 weeks following the initial scan demonstrating progression (see section 5.3.1.). If this repeat scan does not show further progression, imaging frequency can revert to every 8 weeks (+/- 4 days).

K: Only for subjects with tumor that in the opinion of the study treatment team is safely accessible for biopsy.

L: Baseline research blood collection will be collected prior to dosing of any study therapy (visit window day -7 to 0, prior to dosing). Additional on-treatment research bloods will be collected on cycle 1 day 15 (day -4 to 0), on cycle 2 day 1 (day -4 to 0), and at the time of progression (+/- 7 days). No research blood is needed for day 1 of any cycle beyond cycle 2. Research blood samples should be collected and shipped on Monday-Thursday only to avoid problems with weekend/holiday delivery. For additional details, see section 9.3.1.

M: For patients randomized to cobimetinib plus atezolizumab (*study arm B only*).

N: Off-study evaluations will be completed 4 weeks after meeting at least one of the criteria listed in section 5.3.

O: Patients receiving cobimetinib (*study arm B only*).

P: Adverse events will be assessed at least 90 days after the last dose of either study agent. For patients removed due to unacceptable toxicity, they will be followed until resolution of the adverse event.

Q: Scans do not need to be repeated if a scan has been performed within 8 weeks.

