11. MEASUREMENT OF EFFECT

11.1 Antitumor Effect – Solid Tumors

For the purposes of this study, patients should be re-evaluated for response every 8 weeks. Response and progression will be evaluated in this study using the new international criteria proposed by the revised Response Evaluation Criteria in Solid Tumors (RECIST) guideline (version 1.1) (Eisenhauer *et al.*, 2009). Changes in the largest diameter (unidimensional measurement) of the tumor lesions and the shortest diameter in the case of malignant lymph nodes are used in the RECIST criteria.

This study will [also] evaluate response and progression using immune-related response criteria (irRC) (Wolchok *et al.*, 2009). See **Appendix D** for a detailed description of the evaluation criteria.

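### Appendix D makes a final, unconfirmed tumour increase of 25% or more irSD, so some first-scan progressors get a best irRC response of stable disease

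*Combined protocol and SAP*

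**What the plan says.** Section 11.1 of the combined protocol and SAP makes RECIST 1.1 the main standard. It adds that response and progression will also be evaluated by the immune-related response criteria (irRC) in Appendix D.

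Appendix D, Step 6, defines the classes at each assessment:

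- irPD is a rise in tumour burden of at least 25% "relative to nadir confirmed by a consecutive assessment" at least 4 weeks after first documentation.
- irSD is whatever is left: "Criteria for irCR, irPR, and irPD are not met; does not require confirmation".

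The irBOR table returns irSD on "At least one irSD and no irCR and no irPR", and irPD only on "At least one irPD and no irCR, no irPR, and no irSD". Neither table has a row for an unconfirmed irPD or a non-evaluable patient, and irSD has no minimum duration.

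The scan schedule decides who can be confirmed:

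- Section 5.3 lists as a reason to stop treatment "Disease progression not meeting criteria dosing of study treatment beyond disease progression".
- Section 5.3.1 sets the next scan only for those who continue: "Patients treated beyond progression should receive their next follow-up scan 6-8 weeks following the initial assessment of radiological progression". Continuing requires, among other things, clinical benefit as judged by the investigator.
- Section 10, footnote N, places the off-study visit 4 weeks after a stopping criterion is met. Footnote Q says of that visit: "Scans do not need to be repeated if a scan has been performed within 8 weeks".
- Section 5.4 asks for disease status at least every three months afterwards and does not mention imaging.

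**The concern.** Under these rules, a patient whose burden doubles at week 8, who stops treatment and who is not scanned again is recorded as stable. The same patient is PD in the RECIST table of section 11.1.4.3, which asks for no confirming scan, and has a PFS event under section 11.1.6. Section 13.5.2 gives its response categories an unknown or not-assessable option; Appendix D has no counterpart.

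At stake is the progression half of the irRC evaluation promised in section 11.1. Section 13 gives no irRC rules, so Appendix D is the only governing text, and an analyst who follows it would put some rapid progressors under stable disease. Any irRC disease-control figure would be too high, and the contrast between arms could be diluted.

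**Working it through.** **Step 1: the classification.** Take a first post-baseline scan with an increase of 25% or more over nadir and no later scan. irCR and irPR are not met. irPD is not met because confirmation is part of its criterion. The assessment is therefore irSD by the residual rule. With one irSD and no irCR or irPR, irBOR is irSD. This needs no assumption.

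**Step 2: whether the schedule produces such patients.** Someone who progresses and does not qualify to continue stops treatment. The off-study visit follows 4 weeks (±7 days) after the stopping criterion is met. If stopping follows promptly on the scan, that scan is then about 4 weeks old, inside the 8-week waiver, so no new scan is required. No later imaging is stated. Some first-scan progressors will therefore have no confirming scan. How many is not in the documents.

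**Step 3: the planning basis.** The plan gives no irSD or irBOR figure, so the check is on the medians used below. Section 13.2 states 2 versus 4 months, one-sided alpha 0.05, 90% power and 71 events. With hazard ratio 0.5 under exponential PFS, Schoenfeld's formula gives

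4 × (1.645 + 1.282)² / (ln 0.5)² = 71.3 events,

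and 71 events give 89.9% power. The plan's figure reproduces.

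**Step 4: PFS events by the first scan.** The scan is at 8 weeks = 56/30.4375 = 1.84 months. Arm A is taken as the 2-month arm, as the design hypothesis implies, with 38 evaluable patients per arm (section 13.1).

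- Arm A: a = 1 − 0.5^(1.84/2) = 0.471, or 17.9 of 38.
- Arm B: b = 1 − 0.5^(1.84/4) = 0.273, or 10.4 of 38.
- Gap: 19.8 points. Over the ±4-day window the figures are 45–49% versus 26–29%.

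**Step 5: the effect on labels.** Let s be the share of these events that are measured increases of 25% or more with no confirming scan. This is an assumption, taken here as equal in both arms. False irSD is s × a and s × b. The apparent share without irPD is 1 − a(1 − s) and 1 − b(1 − s), so the apparent gap is (1 − s)(a − b).

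| s | False irSD, A vs B | Apparent share without irPD, A vs B | Gap (points) |
|---|---|---|---|
| 0 | 0% vs 0% | 53% vs 73% | 20 |
| 0.25 | 12% vs 7% | 65% vs 80% | 15 |
| 0.5 | 24% vs 14% | 76% vs 86% | 10 |
| 0.75 | 35% vs 20% | 88% vs 93% | 5 |
| 1 (ceiling) | 47% vs 27% | 100% vs 100% | 0 |

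**Step 6: unequal shares.** The apparent contrast reverses only if Arm A's confirmed share (1 − s) is below b/a = 0.273/0.471 = 0.58 of Arm B's. Separately, Arm A has more false irSD labels unless its unconfirmed share s is below 0.58 of Arm B's.

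**Step 7: thresholds.** If lesions grow evenly, a 20% rise in diameter is 1.2² − 1 = 44% in area, so RECIST target-lesion progression would usually pass the 25% irRC threshold. Conversely, 25% in area is about 12% in diameter (√1.25 − 1). A patient between the two has no RECIST target-lesion progression and, while still on treatment, is scanned again at 8 weeks.

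**The case against.** The strongest reply is that no planned analysis uses the affected label. The clinical endpoints are PFS, OS, safety and ORR by RECIST 1.1. PFS has its own dating rule, and section 13 never mentions irRC, irBOR or disease control. irCR and irPR keep their confirmation requirement, so an irRC response rate is not inflated. All of this stands and caps the importance of the point. It does not remove it, because section 11.1 still commits the study to evaluating progression by irRC.

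A reader might also infer more than the documents support:

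- *That 47% and 27% are false-irSD rates.* They are PFS-event probabilities. They include deaths and clinical progression before any scan, where there is no tumour burden to classify. They also include non-target progression, which need not raise a burden that counts only index and measurable new lesions.
- *That the error falls more heavily on the worse arm.* This is an inference from the planning medians and similar unconfirmed shares. Continuing past progression rests on investigator judgement in an open-label trial, so equal shares cannot be presumed.
- *That a true difference would reverse.* With equal shares the gap shrinks to zero at most. Reversal needs the 0.58 condition in Step 6, for which the documents give no evidence.
- *That most first-scan progressors go unconfirmed.* Three-monthly follow-up may supply some scans, and the proportion treated beyond progression is unknown.

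Finally, counting an unconfirmed increase as irPD is a choice; a separate category would also do. That is fair, and the fix uses a separate line.

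**Conclusion.** The concern holds in a limited form. The mislabelling follows directly from the two Appendix D tables, and the scan schedule makes it foreseeable. It affects irSD, irPD and any immune-related disease-control summary, and nothing else.

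Its size cannot be fixed from the documents. The upper bounds are 47% versus 27% of patients, resting on exponential PFS at the planning medians. If half of those events were unconfirmed increases in both arms, 24% versus 14% would be wrongly irSD and a 20-point contrast would read as 10. The supported conclusion is dilution under equal shares. Neither a reversal nor a bias of known direction between the arms is established.

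**What to change.** In Appendix D, Step 6:

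- Restrict irSD to assessments with less than a 50% decrease and less than a 25% increase, or to an increase that a later scan does not confirm.
- Classify a final increase of 25% or more over nadir with no later evaluable assessment as irPD, dated at first documentation. Report it on a separate 'unconfirmed irPD' line and never count that assessment as irSD in irBOR. An earlier genuine irSD still stands.
- Say where an unconfirmed decrease of 50% or more goes, so that narrowing irSD leaves no assessment without a class. Leaving it in irSD, where the present residual rule puts it, would do.

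Section 13 should also say which irRC summaries will be reported. Settling this before irBOR is derived avoids a choice made after the data are seen in an open-label trial.

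The cost is a few lines of text, with no new scans and no change in patient care. The small downside is that a few pseudo-progressors without a later scan count as irPD; the separate line lets a reader see how many patients carry that label.

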APPENDIX E PATIENT MEDICATION DIARY - COBIMETINIB

PATIENT ID	
CYCLE NUMBER	

INSTRUCTIONS TO THE PATIENT:

1. Complete one form for each 4 week-period while you take **cobimetinib**. Each cycle of therapy is 4 weeks (28 days).
2. Take your dose of **cobimetinib** at about the same time each morning for the first 21 days. Do not take cobimetinib on days 22 through 28.
3. Record the date, the number of tablets you took, and when you took them. Record doses as soon as you take them; do not batch entries together at a later time.
4. If you miss taking your dose and remember within 1 hour of your scheduled dose, you may take it late. If it has been more than 1 hour, do not make up the dose; resume dosing with the next scheduled dose. If vomiting occurs, do not make up the dose; resume dosing with the next scheduled dose.
5. Take cobimetinib tablets orally in the morning with or without food. The tablets should be swallowed whole and must not be crushed or broken.
6. If you have any comments or notice any side effects, please record them in the Comments column. If you make a mistake while you write, please cross it out with one line, put your initials next to it, and then write the corrected information next to your initials. Example:
~~10:30 am~~ SB *9:30 am*
7. Please return this form to your physician when you go for your next appointment.

Day	Date	Time of Daily Dose	# of Tablets Taken	Comments
1				
2				
3				
4				
5				
6				
7				
8				
9				
10				
11				
12				
13				
14				
Day	Date	Time of Daily Dose	# of Tablets Taken	Comments

15				
16				
17				
18				
19				
20				
21				
22		Do not take cobimetinib on these days.		
23				
24				
25				
26				
27				
28				
Participant's Signature		Date		

Physician's Office will complete this section:

1. Total number of tablets taken this month (each size)

2. Physician/Nurse/Data Manager's Signature/Date
